#### 4.2 Study Endpoints

#### 4.2.1 Primary Study Endpoints

The primary endpoint will be the ORR of the Nivolumab and BMS-986253 combination, and the ORR of the Nivolumab monotherapy. ORR will be determined based upon RECIST v. 1.1 criteria. The safety of BMS-986253 in combination with Nivolumab will be determined.

#### 4.2.2 Secondary Study Endpoints

The secondary endpoints will include determining the TTR, DOR, PFS, OS, and safety for both treatment arms. These endpoints will allow achievement of the secondary objectives for the study. Thus, these determinations will provide greater insight toward expected clinical response of BMS-986253 when combined with Nivolumab for use in HCC patients. Additionally, potential new insights into the management of side effects and increased safety is possible.

#### 4.2.3 Exploratory Endpoints

Exploratory/translational endpoints will include detailed analysis of fresh pre-treatment and on-treatment (protocol at three months and at time of progression) core biopsies. Our collaboration team at NYU includes the ability to interrogate the TME in a novel, rigorous manner using 30-parameter platforms for single cell flow cytometry. This novel technology also has the ability to "tag" cell subsets/markers and perform single cell RNAseq. Using these techniques, we will aim to discover novel biomarkers predictive of response along with the ability to identify additional novel targets in patients who may "escape" or relapse to known immune oncology therapies.

# 5 Study Enrollment and Withdrawal

Advanced HCC patients who are not eligible for resection or other local-regional therapy, and are eligible for systemic treatment will be considered. Patients must be naïve to other systemic therapies. The study is a phase II design with 50 patients to be randomized 1:1 into the following arms (see Study Schema): Arm 1 (control) Nivolumab 240mg IV every 2 weeks monotherapy; Arm 2 Nivolumab 240 mg IV plus BMS-986253 2400mg IV every 2 weeks. The first six patients will be monitored for Dose Limiting Toxicity in each arm. Dose Limiting Toxicities will be defined by toxicity occurring during the first 4 weeks of treatment on this study. If no drug related AE meeting DLT criteria is observed in any arm in >=4 of 6 patients, the study arms will continue as planned. If >2 out of 6 patients are observed to have related AE (i.e., AE with no clear alternative explanation) meeting DLT criteria that has not been observed in the use of nivolumab monotherapy as described in the package insert, then a lower dose strategy for BMS-986253 (1200 mg IV q 2 weeks) vs. discontinuation of the arm will be implemented in coordination with the DSMC and the study supporter. Should a lower dose strategy be chosen, DLTs will be observed in the first 6 subjects will be observed as above prior to expansion to 25 subjects.

The following will be considered DLTs:

Any grade 4 toxicity

Version: 11.0

• Any grade 3 toxicity, with the exceptions of fatigue; rash that improves to grade 2 with medical management within 3 day; elevations of amylase and lipase in the absence of clinical pancreatitis; elevations in AST, ALT or alkaline phosphatase; nausea, vomiting or diarrhea that improves to grade 2 or lower, with maximal medical management within 3 days; and any grade 3 electrolyte abnormality that is corrected to grade 2 or lower within 48 hours; hypothyroidism that improves to grade 2 with medical management.

Asymptomatic lymphopenia or leukopenia of any grade will NOT be considered a DLT.

Any toxicity fitting the above criteria for the definition of a DLT and with an attribution of "related" to study treatment is required to be considered a DLT.

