#### 4 Study Design and Endpoints

#### 4.1 Description of Study Design

The trial is a phase II, randomized controlled, single blinded study evaluating 2 study arms: Arm 1 (control) Nivolumab 240mg IV every 2 weeks monotherapy; Arm 2 Nivolumab 240 mg IV plus BMS-986253 2400 mg IV every 2 weeks(see Study Schema). Six patients will be observed for toxicity in each arm The trial will be performed at two sites. Holding of dose will occur if a dose limiting toxicity occurs on any arm.

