#### 6.1.7 Dose Adjustments/Modifications/Delays

Recommendations for study drug modifications are provided in the tables below. The recommendations for Nivolumab monotherapy are from the Package Insert. Since no dose limiting toxicity has been observed for BMS-986253 monotherapy in phase I (Investigator Brochure) and the combination of Nivolumab and BMS-986253 is currently being evaluated in CA027-002 with no new safety signals noted,

Version: 11.0

the management plan for toxicity will be the same as for Nivolumab monotherapy however both agents will be withheld or discontinued based on the described AEs below.

There are no recommended dose modifications for hypothyroidism or hyperthyroidism.

Interrupt or slow the rate of infusion in patients with mild or moderate infusion reactions. Discontinue the study drug in patients with severe or life-threatening infusion reactions.

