# ADVERSE EVENT MANAGEMENT FOR NIVOLUMAB MONOTHERAPY OR FOR NIVOLUMAB IN COMBINATION WITH BMS-986253

Adverse Reaction	Severity*	Dose Modification
	Grade 2 diarrhea or colitis	Withhold dose a
Colitis	Grade 3 diarrhea or colitis	Withhold dose when single
		agent (Nivolumab
		monotherapy), Permanently
		discontinue when administered
		with additional study drug
	Grade 4 diarrhea or colitis	Permanently discontinue
Pneumonitis	Grade 2 pneumonitis	Withhold dose a
	Grade 3 or 4 pneumonitis	Permanently discontinue
	If AST/ALT is within normal	
	limits at baseline and increases	
	to more than 3 and up to 5 times	
	ULN	
Hepatitis	If AST/ALT is more than 1 and	Withhold dose b
	up to 3 times ULN at baseline	
	and increases to more than 5	
	and up to 10 times ULN	
	If AST/ALT is more than 3 and	
	up to 5 times ULN at baseline	
	and increases to more than 8	
	and up to 10 times ULN	
	If AST or ALT increase to more	Permanently discontinue
	than 10 times the ULN or total	
	bilirubin increases to more than	
	3 times the ULN	
Hypophysitis	Grade 2 or 3 hypophysitis	Withhold dose a
	Grade 4 hypophysitis	Permanently discontinue
Adrenal Insufficiency	Grade 2 adrenal insufficiency	Withhold dose a
	Grade 3 or 4 adrenal	Permanently discontinue
T 15:1 1 M 10:	insufficiency	145
Type I Diabetes Mellitus	Grade 3 hyperglycemia	Withhold dose a
	Grade 4 hyperglycemia	Permanently discontinue
Nephritis and Renal Dysfunction	Serum Cr more than 1.5 and up	Withhold dose a
	to 6 times the ULN	
	Serum Cr more than 6 times the	Permanently discontinue
	ULN	
Skin	Grade 3 rash or suspected	Withhold dose a
	Stevens-Johnson syndrome	
	(SJS) or toxic epidermal	
	necrolysis (TEN)	D " "
	Grade 4 rash or confirmed SJS	Permanently discontinue
- L PC	or TEN	Maria I I I I I
Encephalitis	New-onset moderate or severe	Withhold dose a
	neurologic signs or symptoms	

Version: 11.0

	Immune-mediated encephalitis	Permanently discontinue
	Other Grade 3 adverse reaction	Withhold dose a
	First Occurrence	
	Recurrence of same Grade 3	Permanently discontinue
	Adverse reactions	
	Life threatening or Grade 4	Permanently discontinue
	adverse reaction	
Other	Grade 3 myocarditis	Permanently discontinue
	Requirement for 10 mg per day	Permanently discontinue
	or greater prednisone or	
	equivalent for more than 12	
	weeks	
	Grade 2 or 3 adverse reactions	Permanently discontinue
	lasting 12 weeks or longer	

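### For Arm 2, Section 5 keeps out of the DLT count some events for which the Section 6.1.7 table permanently stops both drugs, so the six-patient check can record no DLT for a participant already off treatment

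*Combined protocol and SAP*

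**What the plan says.** **DLT definition (Section 5).** The window is fixed: "Dose Limiting Toxicities will be defined by toxicity occurring during the first 4 weeks of treatment on this study". The list has two items. The first is "Any grade 4 toxicity". The second is any grade 3 toxicity, less a set of exceptions that includes "elevations in AST, ALT or alkaline phosphatase; nausea, vomiting or diarrhea that improves to grade 2 or lower, with maximal medical management within 3 days". The list then adds: "Asymptomatic lymphopenia or leukopenia of any grade will NOT be considered a DLT". A listed toxicity must also be attributed to study treatment. No item mentions a fatal toxicity.

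**Decision rule.** Under Section 5, the arms continue if at least 4 of 6 have no drug-related event meeting DLT criteria. If more than 2 of 6 have such an event, and it is not one already described for nivolumab monotherapy in the package insert, a lower-dose strategy or closing the arm follows. Section 10.4.4 repeats the action condition, but its continue condition refers to any treatment-related event, without requiring that it meet DLT criteria.

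**Treatment discontinuation (Section 6.1.7).** The text says "the management plan for toxicity will be the same as for Nivolumab monotherapy however both agents will be withheld or discontinued" on the basis of the table. For grade 3 diarrhea or colitis, the Colitis row withholds nivolumab given alone but permanently discontinues when it is given "with additional study drug". The Hepatitis row that begins "If AST or ALT increase to more" sets permanent discontinuation above 10 times ULN. The Other rows permanently discontinue for a grade 4 reaction.

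**Elsewhere.** Section 4.1 says: "Holding of dose will occur if a dose limiting toxicity occurs on any arm". Section 8.9 halts study agent at four events that are grade 4 or require permanent discontinuation, if rated probably related.

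**The concern.** A DLT count is meant to show whether the combination can be given at the planned dose. Here an event that ends a participant's treatment for good under one section can be classed as not dose-limiting under another. The six-patient count is the rule that the protocol ties to lowering BMS-986253 or closing Arm 2, and safety of the combination is stated together with the primary endpoint (Sections 3.1 and 4.2.1). If the count omits permanent stops, those making the decision could see a clean run-in while participants have already lost access to both drugs. The two statements of the continue condition add a second difficulty: the same data can satisfy one and fail the other.

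**Working it through.** The plan states no operating characteristics for this check, so there is no figure to reproduce. The main check is a comparison of the texts.

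**Step 1. Arm 2 events in the first 4 weeks, side by side.**

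| Event | Section 5 | Section 6.1.7 table | Conflict |
|---|---|---|---|
| Grade 3 diarrhea, down to grade 2 or lower within 3 days | Not a DLT | Permanent stop, both drugs | Yes, from the documents alone |
| Asymptomatic grade 4 lymphopenia or leukopenia | Never a DLT | Permanent stop for a grade 4 reaction | Yes, where the result is recorded as an adverse reaction (Section 8.1.1 says when an abnormal result is an adverse event) |
| Grade 3 AST/ALT above 10 times ULN | Not a DLT; no ceiling or time limit | Permanent stop | Depends on the upper limit U of grade 3: yes if U is above 10 times ULN, none if U is 10 or less |
| Grade 3 rash improving within 3 days | Not a DLT | Withhold | None |

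The table is graded by CTCAE version 5.0, whose cut-offs are not reproduced, so the third row rests on an assumption. Grade 4 AST/ALT elevations still count as DLTs.

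**Step 2. The counting rule.** With d participants having a DLT, the Section 5 continue condition is 6 − d ≥ 4, that is d ≤ 2. An event in the first row adds 0 to d and 1 to the number permanently off both drugs.

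**Step 3. The two continue conditions.** Suppose 3 of 6 in Arm 2 have only related grade 3 diarrhea that improves within 3 days.
- Section 5: d = 0, so the arm continues as planned.
- Section 10.4.4, read literally: only 3 of 6 are free of a treatment-related event, so the continue condition fails. The action condition is not met either, because none meets DLT criteria. No outcome is specified.

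**Step 4. The action trigger.** It counts only DLT-criteria events not described for nivolumab in the package insert. Section 2.4.1, citing the nivolumab HCC study and the insert, reports AST, ALT and gastrointestinal events, including grade 3-4. On that reading, diarrhea and AST/ALT events might not count toward the trigger even if the exceptions were removed.

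**Step 5. Illustration for the unfiltered Section 5 continue condition only.** P(condition fails) = 1 − [(1−p)^6 + 6p(1−p)^5 + 15p²(1−p)^4].

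Assume a listed-DLT rate of 10% or 20%. For exempt events add the Section 2.4.1 grade 3-4 rates on nivolumab: AST 3.2% + ALT 2.6% + other GI 1.3% = 7.1%, taking no overlap.

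| Listed DLT rate | Fails, listed only | Fails, exempt events also counted |
|---|---|---|
| 10% | p = 0.100: 1.6% | p = 0.171: 6.7% |
| 20% | p = 0.200: 9.9% | p = 0.271: 20.4% |

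The 7.1% is not limited to 4 weeks and includes events that would not end treatment, as well as grade 4 events that already count. It therefore overstates the exempt treatment-ending rate for nivolumab alone. The rate for the combination is unknown. Failing the continue condition is not the same as meeting the action trigger.

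**The case against.** The strongest reply is that a DLT list drives a cohort decision while the table drives individual care, so the two need not match. That is fair in principle, but nothing in the protocol says the difference is intended, and Section 10.4.4 does not follow the Section 5 list in its continue condition.

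Other safeguards exist. Section 8.9 counts events requiring permanent discontinuation. It needs four of them across the study, rated probably related (a category missing from the two-level scale in Section 8.2.2), is not arm-specific, and cites Section 6.1.8 although the table is in 6.1.7. Section 9.1 gives the DSMC dose modifications, adverse events and deaths, but on a quarterly cycle not tied to the six-patient decision. These are partial backstops, and they stand as such.

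A reader might infer three stronger things that the documents do not support:
- That all six in Arm 2 could plausibly stop with a DLT count of zero. The wording permits it, but it is a logical extreme. Section 2.4.1 describes treatment-attributable events on the combination as grade 1-2, with one discontinuation, for a grade 4 infusion reaction.
- That the exceptions greatly lower the chance of a dose reduction. The package-insert filter in Step 4 blocks that inference.
- That a fatal toxicity would escape notice. The list does not name one, but many would read it as included with grade 4, and Section 8.5 requires deaths to be reported within 24 hours.

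The remaining wording conflicts are secondary. Holding a dose in Section 4.1 may be only a first step. The Section 6.1.7 statement that management matches monotherapy is qualified in the same sentence and defers to the table.

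**Conclusion.** The contradiction is real. For quickly improving grade 3 diarrhea in Arm 2, the documents alone prove it. For asymptomatic grade 4 lymphopenia or leukopenia, it holds when the finding is recorded as an adverse reaction. For AST/ALT, it holds only if grade 3 extends above 10 times ULN. As a result, the six-patient check can record no DLT for participants permanently taken off both drugs, and Sections 5 and 10.4.4 can lead to different conclusions from the same data.

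The size is modest and uncertain. The effect on the action trigger is limited and cannot be calculated from the documents; the Step 5 figures rest on assumed rates and concern only the continue condition. The point still merits correction because it bears on participant safety and on a stated primary aim, and because neither the halting rule nor quarterly review brings permanent stops by arm into the 4-week decision.

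**What to change.** 1. Reconcile Sections 4.1, 5, 6.1.7, 8.9 and 10.4.4 so that one event is not both outside the dose-limiting list and a cause of permanent discontinuation, or state that the difference is intended and why. Which clinical rule applies is for the sponsor and investigators; this review takes no position.
2. Use one continue condition in Sections 5 and 10.4.4, and say what happens when neither the continue nor the action condition is met.
3. State how a related fatal event is treated in the count.
4. In Section 8.9, correct the cross-reference and align the attribution term with Section 8.2.2.
5. Whatever reading is chosen, report to the DSMC at the six-patient decision, beside the DLT count, the number of the first six in each arm who permanently stopped under Section 6.1.7 within 4 weeks.

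The cost is a wording amendment and one extra report line from data already recorded. The downside is possibly more frequent review. The documents do not say whether the run-in is over; if it is, item 5 can still be tabulated from existing records and written into the formal SAP, which Section 10.1 requires before database lock.

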#### 5.1 Inclusion Criteria

In order to be eligible to participate in this study, an individual must meet all of the following criteria:

- 1. Have histologically confirmed evidence of HCC, Childs-Pugh score of ≤7.
  - a. Participants must be willing to provide specimen from fresh, pre- and on-treatment tumor core biopsies for histologic diagnosis and translational studies.
- 2. Radiographically measurable disease by RECIST1.1 in at least one site.
- 3. Deemed to not be a candidate for resection or other local-regional therapy.
- 4. Must not be receiving treatment with other investigational agents and must not have received any other systemic therapy prior to registration.
  - a. Prior radioembolization, local ablative therapies (radiofrequency, microwave or cryoablation), radiation (external beam or stereotactic), or hepatic resection permitted if completed ≥ 4 weeks prior to study enrollment and if patient has recovered with ≤ grade 1 toxicity and if untreated measurable disease is present.
- 5. Be willing and able to provide written informed consent/assent for the trial.
- 6. Participants must be ≥ 18 years
- 7. Have a Eastern Cooperative Oncology Group (ECOG) performance status of 0-1
- 8. If hepatitis B is present, participants must be on anti-viral HBV therapy.
- All women of childbearing potential (not surgically sterilized and between menarche and 1
  year post menopause) must have a blood test to rule out pregnancy within 24 hours prior to
  start of study treatment
- 10. All women of childbearing potential must agree to follow instructions for method(s) of contraception for the duration of treatment with study treatment (s) and for 4 months following discontinuation of study treatment.
- 11. Male participants must not donate sperm during this period.
- 12. Demonstrate adequate organ function as defined by the following required lab and acceptable range criteria:

Adequate bone marrow function:

Absolute neutrophil count > 1000/mcLPlatelet count > 50,000/mcLHemoglobin > 8.5 g/dL

Adequate hepatic function:

Total bilirubin < 2 mg/dL or < 1.5 times upper limit of normal

(ULN)

AST and ALT  $\leq$  5 times ULN INR  $\leq$  1.5 times ULN Albumin > 2.8 g/dL

Adequate renal function:

Creatinine < 2.0 mg/DI

#### 5.2 Exclusion Criteria

An individual who meets any of the following criteria will be excluded from participation in this study:

Version: 11.0

1. Women who are pregnant or breastfeeding.

- 2. Presence of other malignancies. Participants with active second malignancy other than non-melanoma skin cancer or cervical carcinoma in situ. NOTE: Patients with history of malignancy are not considered to have a "currently active" malignancy if they have completed therapy and are now considered by their physician to be at less than 30% risk for relapse.
- 3. Have active or history of Tuberculosis
- 4. Participants with known HIV positive status
- 5. Participants with known CNS metastases
- 6. Uncontrolled ascites
- 7. Uncontrolled encephalopathy
- 8. Uncontrolled gastro-esophageal varices. Prior organ allograft or allogeneic bone marrow transplantation
- 9. Participants with active, known, or suspected autoimmune disease. Participants with vitiligo, type I diabetes mellitus, residual hypothyroidism due to autoimmune condition only requiring hormone replacement, euthyroid participants with a history of Grave's disease (participants with suspected autoimmune thyroid disorders must be negative for thyroglobulin and thyroid peroxidase antibodies and thyroid stimulating immunoglobulin prior to first dose of study treatment), psoriasis not requiring systemic treatment, or conditions not expected to recur in the absence of an external trigger are permitted to enroll.
- 10. Participants with a condition requiring systemic treatment with either corticosteroids (> 10 mg daily prednisone equivalents) or other immunosuppressive medications within 14 days of study treatment administration except for adrenal replacement steroid doses > 10 mg daily prednisone equivalent in the absence of active autoimmune disease. Note: Treatment with a short course of steroids (< 5 days) up to 7 days prior to initiating study treatment is permitted.

- 11. Interstitial lung disease that is symptomatic or may interfere with the detection or management of suspected treatment-related pulmonary toxicity.
- 12. Uncontrolled or significant cardiovascular disease including, but not limited to, any of the following:
  - -Myocardial infarction or stroke/transient ischemic attack within the past 6 months
  - -Uncontrolled angina within the past 3 months
  - -Any history of clinically significant arrhythmias (such as ventricular tachycardia, ventricular fibrillation, or torsades de pointes)
  - -History of other clinically significant heart disease (eg, cardiomyopathy, congestive heart failure with New York Heart Association functional classification III to IV, pericarditis, significant pericardial effusion, or myocarditis)
  - -Cardiovascular disease-related requirement for daily supplemental oxygen therapy.
- 13. Participants with ongoing or active, uncontrolled infections (afebrile for ≥ 48 hours off antibiotics). If hepatitis B is present, must be on anti-viral HBV therapy.
- 14. Must not have a psychiatric illness, other significant medical illness, or social situation, which, in the investigator's opinion, would limit compliance or ability to comply with study requirements.
- 15. Any major surgery within 4 weeks of study treatment. Participants must have recovered from the effects of major surgery or significant traumatic injury at least 14 days before
- 16. Any uncontrolled inflammatory disease including Crohn's disease and ulcerative colitis
- 17. Treatment with botanical preparations (eg, herbal supplements, including potential drugs of abuse, or traditional Chinese medicines) intended for general health support or to treat the disease under study within 2 weeks prior to randomization/treatment.
- 18. Concomitant use of statins while on study.
- 19. Current or history of clinically significant muscle disorders (eg, myositis), recent unresolved muscle injury, or any condition known to elevate serum CK levels.
- 20. Known history of sensitivity to infusions containing Tween 20 (polysorbate 20) and Tween 80 (polysorbate 80).
- 21. Participants who have received a live / attenuated vaccine within 30 days of first treatment.

Version: 11.0

22. Concomitant use of any live / attenuated vaccine during treatment and until 100 days following last dose.

#### 5.3 Inclusion of Women and Minorities

Both men and women of all races and ethnic groups are eligible for this trial.

#### 5.4 Vulnerable Subjects

Vulnerable subjects will not be eligible for enrollment into the study.

